7.2.1.6 Assignment of Screening Number

All consented subjects will be given a unique screening number that will be used to identify the subject for all procedures that occur prior to randomization or allocation. Each subject will be assigned only one screening number. Screening numbers must not be re-used for different subjects.

Any subject who is screened multiple times will retain the original screening number assigned at the initial screening visit.

7.2.1.7 Trial Compliance (Medication/Diet/Activity/Other)

Interruptions from the protocol specified treatment plan for greater than 12 weeks between pembrolizumab doses in the post-operative setting require consultation between the investigator and the Sponsor-Investigator and written documentation of the collaborative decision on subject management. Any delay in resumption of study related therapy beyond 12 weeks from surgery will also be reviewed in consultation between the investigator and Sponsor-Investigator.

Administration of trial medication will be witnessed by the investigator and/or trial staff while the subject is in the treatment center. Administration of chemotherapy including oral and IV chemotherapy will be administered as per standard practice without additional verification.

7.2.2 Clinical Procedures/Assessments

7.2.2.1 Adverse Event (AE) Monitoring

The investigator or qualified designee will assess each subject to evaluate for potential new or worsening AEs as specified in the Trial Flow Chart and more frequently if clinically indicated. Adverse experiences will be graded and recorded throughout the study and during the follow-up period according to NCI CTCAE Version 4.0 (see Section 13.2). Toxicities will be characterized in terms regarding seriousness, causality, toxicity grading, and action taken with regard to trial treatment.

Please refer to section 7.3 for detailed information regarding the assessment and recording of AEs.

7.2.2.2 Physical Exam

The investigator or qualified designee will perform a complete physical exam during the screening period. Clinically significant abnormal findings should be recorded as medical history. A full physical exam should be performed as specified in the Trial Flow Chart. For cycles that do not require a full physical exam per the Trial Flow Chart, the investigator or qualified designee will perform a directed physical exam as clinically indicated prior to dosing on Day 1 of each treatment cycle.

After the first dose of trial treatment new clinically significant abnormal findings should be recorded as AEs.

7.2.2.3 Vital Signs

The investigator or qualified designee will take vital signs at screening, prior to the administration of each dose of trial treatment and at treatment discontinuation as specified in the Trial Flow Chart (Section 6.0). Vital signs should include temperature, pulse, respiratory rate, weight and blood pressure. Height will be measured at screening only.

7.2.2.4 12-Lead Electrocardiogram

A standard 12-lead ECG will be performed using local standard procedures once at screening. Clinically significant abnormal findings should be recorded as medical history. Additional time points may be performed as clinically necessary.

Please note that the ECHO is only required for patients receiving Epirubicin.

7.2.2.5 2-D Echocardiogram

A standard 2-dimensional Echocardiogram (TTE) will be performed using local standard procedures once at screening to assess left ventricular ejection fraction (EF) to determine eligibility for Epirubicin chemotherapy. Additional Echocardiograms will be conducted during therapy and as clinically necessary as described in the Trial Flow Chart.

7.2.2.6 Eastern Cooperative Oncology Group (ECOG) Performance Scale

The investigator or qualified designee will assess ECOG status (see Section 13.1) at screening, prior to dosing on Day 1 of each treatment cycle (except Cycle 1) and at discontinuation of trial treatment as specified in the Trial Flow Chart.

7.2.2.7 Tumor Imaging and Assessment of Disease

Tumor imaging may be performed by computed tomography (CT) including PET/CT (preferred) or magnetic resonance imaging (MRI), but the same imaging technique, acquisition, and processing parameters should be used in a subject throughout the trial. If PET/CT was used initially it is not required to use PET/CT for each subsequent tumor imaging assessment, CT is sufficient.

Imaging tests will be reviewed locally and tumors will be quantified utilizing RECIST 1.1. All treatment decisions will be made locally by the treating Investigator's radiographic assessment of disease.

7.2.2.7.1 Baseline Tumor Imaging

To meet screening criteria, subjects do not require measurable disease on imaging. However, if subjects have a lesion quantifiable according to RECIST 1.1 criteria, this will be utilized to assess disease response (RR).

Scans performed as part of routine clinical management are acceptable for use as the baseline scan if they are of diagnostic quality and performed within 28 days prior to the first dose of study treatment.

7.2.2.7.2 Tumor Imaging During Trial

The first on-study imaging assessment will be performed 11 weeks after Cycle 1 Day 1 (78 days +/- 14 days) and will be used to assess response to chemotherapy and eligibility for surgery. Imaging may be conducted prior to Cycle 4 dosing (of Pembrolizumab) if clinically indicated as assessed by local routine practice. Subsequent imaging will be performed

following surgical resection and will begin within 7 days of Cycle 5 day 1 (first post-operative cycle) which is expected to not be later than 8 weeks from the time of surgery (65 days +/- 14 days). Beginning from the first post-operative scan, subsequent tumor imaging will be performed every 12 weeks (+/- 7 days).

Imaging should continue to be performed until whichever one of the following occurs first:

- disease progression limiting a subject from surgical resection
- recurrence of disease following surgical resection
- completion of study treatment
- withdrawal of consent
- death
- end of study

Imaging should follow calendar days and not be delayed for any dose interruptions that may occur (except for delays post-operatively).

7.2.2.7.3 Assessment of Disease- RECIST 1.1 and irRECIST

The primary endpoints in this study are recurrence free survival and pathologic surgical response, and not tumor response based on RECIST. In addition due to the neo-adjuvant nature of the study, it is not expected to have confirmatory scans of response prior to surgery. Thus all responses will be unconfirmed and we do not anticipate using irRECIST measurements.

7.2.2.8 Tumor Tissue Collection and Correlative Studies Blood Sampling

Tumor tissue sample may be collected in either formalin solution or FFPE block is acceptable. A fine needle aspirate (FNA) or cytologic specimen will not be acceptable.

Details regarding time points for collection of tumor tissue are outlined in the Study Flow Chart –Section 6.0.

7.2.3 Laboratory Procedures/Assessments

Details regarding specific laboratory procedures/assessments to be performed in this trial are provided below

7.2.3.1 Laboratory Safety Evaluations (Hematology, Chemistry and Urinalysis)

Laboratory tests for hematology, chemistry, urinalysis, and others are specified in Table 7.

Table 7 Laboratory Tests

Hematology	Chemistry	Urinalysis	Other
Hematocrit	Albumin	Blood	Serum β -human chorionic gonadotropin†
Hemoglobin	Alkaline phosphatase	Glucose	(β -hCG)†
Platelet count	Alanine aminotransferase (ALT)	Protein	PT (INR)
WBC (total and differential)	Aspartate aminotransferase (AST)	Specific gravity	aPTT
Red Blood Cell Count	Lactate dehydrogenase (LDH)	Microscopic exam (If abnormal)	Total triiodothyronine (T3)
Absolute Neutrophil Count	Carbon Dioxide ‡	results are noted	Free tyroxine (T4)
Absolute Lymphocyte Count	(CO_2 or bicarbonate)	Urine pregnancy test †	Thyroid stimulating hormone (TSH)
	Uric Acid		
	Calcium		
	Chloride		Blood for correlative studies
	Glucose		
	Phosphorus		
	Potassium		
	Sodium		
	Magnesium		
	Total Bilirubin		
	Direct Bilirubin (If total bilirubin is elevated above the upper limit of normal)		
	Total protein		
	Blood Urea Nitrogen		

† Perform on women of childbearing potential only. If urine pregnancy results cannot be confirmed as negative, a serum pregnancy test will be required.

‡ If considered standard of care in your region.

Laboratory tests for screening should be performed within 14 days of dosing for eligibility. If performed more than 72 hours prior to Cycle 1 Day 1 they should be repeated on Cycle 1 Day 1 prior to the first dose of treatment for treatment decisions but not for eligibility. After Cycle 1, pre-dose laboratory procedures can be conducted up to 72 hours prior to dosing. Results of standard tests must be reviewed by the investigator or qualified designee per local treating guidelines and found to be acceptable prior to each dose of trial treatment.

7.2.4 Other Procedures

7.2.4.1 Withdrawal/Discontinuation

When a subject discontinues/withdraws prior to trial completion, all applicable activities scheduled for the final trial visit should be performed at the time of discontinuation. Any adverse events which are present at the time of discontinuation/withdrawal should be followed in accordance with the safety requirements outlined in Section 7.3 - Assessing and Recording Adverse Events.

7.2.4.2 Blinding/Unblinding

This is an open label trial; there is no blinding for this trial.

7.2.5 Visit Requirements

Visit requirements are outlined in Section 6.0 - Trial Flow Chart. Specific procedure-related details are provided above in Section 7.2 - Trial Procedures.

7.2.5.1 Screening

Within 28 days prior to expected start of therapy, potential subjects will be evaluated to determine that they fulfill the entry requirements as set forth in Section 5.1. Visit requirements are outlined in Section 6.0 – Trial Flow Chart.

Results of a test performed prior to the subject signing consent as part of routine clinical management are acceptable in lieu of a screening test if performed within the specified time frame. Screening procedures are to be completed within 28 days prior to the first dose of trial treatment except for the following:

- For women of reproductive potential, a urine pregnancy test will be performed within 72 hours prior to the first dose of trial treatment.
- Biopsy collections may be collected up to 42 days prior to the first dose of trial treatment as presented in Section 5.1.1.

Subjects may be rescreened after initially failing to meet the inclusion/exclusion criteria. Results from assessments performed during the initial screening period are acceptable in lieu of a repeat screening test if performed within the specified time frame and the inclusion/exclusion criteria is met.

7.2.5.2 Treatment Period

As described in Section 6.0- Trial Flow Chart, the study treatment period is divided into the pre-operative period, the post-operative combination period, and the maintenance period.

7.2.5.2.1 Pre-operative Treatment Period

This will begin on Cycle 1 Day 1 and as outlined will include 4 cycles of therapy. The first 3 cycles will consist of combination chemotherapy and Pembrolizumab and the 4th cycle will consist of study treatment alone with Pembrolizumab. Based on previous studies it is anticipated that subjects will proceed to surgery between 4-6 weeks following completion of perioperative chemotherapy (completion of cycle 3). The pre-operative treatment period will complete once a subject proceeds to surgical exploration.

All subjects will remain on study if they have received a single dose of study medication, even if they did not complete the full course of pre-surgical chemotherapy or combination therapy.

7.2.5.2.2 Post-operative Treatment Period

All subjects who have received at least 1 dose of pre-surgery study medication will be included in the post-treatment therapy. Subjects will be re-evaluated by the treating Investigator between 4-8 weeks post-operatively per local practice. It is anticipated that the majority of subjects will be deemed appropriate to begin chemotherapy within 8 weeks of surgery but subjects may be delayed at the discretion of the treating physician. The decision to modify chemotherapy (to omit or dose reduce agents) will also be at the discretion of the treating physician and will be documented in the patient record. If delay in post-operative chemotherapy is anticipated beyond 9 weeks, subjects may begin therapy with Pembrolizumab alone and add chemotherapy with subsequent cycles. No subject will receive more than 3 cycles of chemotherapy following surgery.

Disease assessment with CT (or MRI) will be performed prior to initiation of Cycle 5 Day 1 (within 14 days). The first dose of Pembrolizumab after surgery will be Cycle 5 Day 1 and all subsequent dosing will be based on this date.

7.2.5.2.3 Maintenance Treatment Period

Subjects will continue receiving study drug with Pembrolizumab for up to 17 cycles post-operatively with 21 day cycles. The first 3 cycles will be scheduled to be administered with chemotherapy and 14 subsequent cycles will be given with Pembrolizumab alone. If a subject is not deemed appropriate for chemotherapy (per treating physician) that subject will begin Pembrolizumab alone and may receive chemotherapy subsequently for up to 3 cycles per standard practice. Chemotherapy does not need to be given on the same day as Pembrolizumab (if delayed) but all cycles will follow Pembrolizumab dosing. During this treatment period, subjects will continue receiving disease assessment with imaging at 12 week intervals.

7.2.5.3 Post-Treatment Visits

7.2.5.3.1 Safety Follow-Up Visit

The mandatory Safety Follow-Up Visit should be conducted approximately 30 days after the last dose of trial treatment or before the initiation of a new anti-cancer treatment, whichever comes first. All AEs that occur prior to the Safety Follow-Up Visit should be recorded. Subjects with an AE of Grade > 1 will be followed until the resolution of the AE to Grade 0-1 or until the beginning of a new anti-neoplastic therapy, whichever occurs first. SAEs that occur within 90 days of the end of treatment or before initiation of a new anti-cancer treatment should also be followed and recorded.

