2.0 TRIAL DESIGN

2.1 Trial Design

This is a non-randomized, multi-site, open-label trial of pembrolizumab and chemotherapy in subjects with gastric or gastroesophageal junction adenocarcinoma. Up to 38 subjects may be enrolled in a single cohort, for a sample of 28 evaluable subjects, to assess the efficacy of combination therapy with standard peri-operative chemotherapy in resectable gastric or GE junction adenocarcinoma. The trial was initiated at 2 sites and two additional sites were subsequently added to increase enrollment.

All study subjects will receive standard of care chemotherapy for 3 cycles prior to and 3 cycles following surgery in combination with Pembrolizumab with an additional cycle of Pembrolizumab (4 total) in the pre-operative period. Additionally, subjects will complete 12 months of maintenance Pembrolizumab (14 additional doses to complete 17 post-operative cycles) following completion of post-operative chemotherapy. The primary efficacy endpoint will be **pathologic complete response (pCR) rate** among all enrolled subjects. Recurrence or disease progression will be determined based on RECIST 1.1 and investigator assessment.

Adverse events will be monitored throughout the trial and graded in severity according to the guidelines outlined in the NCI Common Terminology Criteria for Adverse Events (CTCAE) version 4.0.(As referenced in Appendix 13.2)

After the end of treatment, each subject will be followed for 30 days for adverse event monitoring. Serious adverse events and Events of Clinical Interest (ECI) will be collected for 90 days after the end of treatment or 30 days after the end of treatment if the subject initiates new anticancer therapy, whichever is earlier. Subjects who discontinue treatment for reasons other than disease recurrence will have post-treatment follow-up for disease status until disease recurrence, withdrawing consent, or becoming lost to follow-up. All subjects will be contacted by telephone for overall survival until death, withdrawal of consent or the end of the study, whichever comes first.

[figure not shown]

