5.2.1.2.1 Dose Modification for Pembrolizumab

Adverse events (both non-serious and serious) associated with pembrolizumab exposure may represent an immunologic etiology. These adverse events may occur shortly after the first dose or several months after the last dose of treatment. Pembrolizumab must be withheld for drug-related toxicities and severe or life-threatening AEs as per Table 4 below. Pembrolizumab will be permanently discontinued for any severe or Grade 3 (grade 2 for pneumonitis) drug-related AE that recurs or any life-threatening event. See Section 5.6 for supportive care guidelines, including use of corticosteroids.

Table 4 Dose Modification Guidelines for Drug-Related Adverse Events for Pembrolizumab

Toxicity	Hold Treatment For Grade	Timing for Restarting Treatment	Treatment Discontinuation
Diarrhea/Colitis	2-3	Toxicity resolves to Grade 0-1	Toxicity does not resolve within 12 weeks of last dose or inability to reduce corticosteroid to 10 mg or less of prednisone or equivalent per day within 12 weeks
	4	Permanently discontinue	Permanently discontinue
AST, ALT, or Increased Bilirubin	2	Toxicity resolves to Grade 0-1	Toxicity does not resolve within 12 weeks of last dose
	3-4	Permanently discontinue (see exception below) ^a	Permanently discontinue
Type 1 diabetes mellitus (if new onset) or Hyperglycemia	T1DM or 3-4	Hold pembrolizumab for new onset Type 1 diabetes mellitus or Grade 3-4 hyperglycemia associated with evidence of beta cell failure	Resume pembrolizumab when patients are clinically and metabolically stable

Toxicity	Hold Treatment For Grade	Timing for Restarting Treatment	Treatment Discontinuation
Hypophysitis	2-4	Toxicity resolves to Grade 0-1. Therapy with pembrolizumab can be continued while endocrine replacement therapy is instituted	Toxicity does not resolve within 12 weeks of last dose or inability to reduce corticosteroid to 10 mg or less of prednisone or equivalent per day within 12 weeks
Hyperthyroidism	3	Toxicity resolves to Grade 0-1	Toxicity does not resolve within 12 weeks of last dose or inability to reduce corticosteroid to 10 mg or less of prednisone or equivalent per day within 12 weeks
	4	Permanently discontinue	Permanently discontinue
Hypothyroidism		Therapy with pembrolizumab can be continued while thyroid replacement therapy is instituted	Therapy with pembrolizumab can be continued while thyroid replacement therapy is instituted

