5.8 Subject Withdrawal/Discontinuation Criteria

Subjects may withdraw consent at any time for any reason or be dropped from the trial at the discretion of the investigator should any untoward effect occur. In addition, a subject may be withdrawn by the investigator or the Sponsor-Investigator if enrollment into the trial is inappropriate, the trial plan is violated, or for administrative and/or other safety reasons. Specific details regarding discontinuation or withdrawal are provided in Section 7.1.4 – Other Procedures.

Even if a subject discontinues trial treatments, they will be encouraged to continue to participate in collection of data regarding the endpoints, including DFS and OS.

A subject must be discontinued from the trial treatments for any of the following reasons:

- The subject or legal representative (such as a parent or legal guardian) withdraws consent.
- Confirmed radiographic disease progression or recurrence
- Unacceptable adverse experiences as described in Section 5.2.1.2
- Intercurrent illness that prevents further administration of treatment
- Investigator's decision to withdraw the subject
- The subject has a confirmed positive serum pregnancy test
- Noncompliance with trial treatment or procedure requirements
- The subject is lost to follow-up
- Completed 12 months of uninterrupted treatment with pembrolizumab following surgical resection or 17 administrations of study medication, whichever is later.

Note: 12 months of study medication is calculated from the date of first dose following surgical resection.

- Administrative reasons

The End of Treatment and Follow-up visit procedures are listed in Section 6.0 (TRIAL FLOW CHART) and Section 7.1.5 (Visit Requirements). After the end of treatment, each subject will be followed for 30 days for adverse event monitoring (serious adverse events will be collected for 90 days after the end of treatment as described in Section 7.2.3.1). Subjects who discontinue for reasons other than progressive disease will have post-treatment follow-up for disease status until disease progression or recurrence, withdrawing consent or becoming lost to follow-up. After documented disease progression each subject will be followed by telephone for overall survival until death, withdrawal of consent, or the end of the study, whichever occurs first.

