7.2.5.3.2 Survival Follow-up

Once a subject experiences confirmed disease progression or completes 17 cycles of post-operative therapy, the subject moves into the survival follow-up phase and should be contacted by telephone every 12 weeks to assess for survival status until death, withdrawal of consent, or the end of the study, whichever occurs first.

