From the time of treatment allocation/randomization through 30 days following cessation of treatment, all adverse events must be reported by the investigator. Such events will be recorded at each examination on the Adverse Event case report forms/worksheets. The reporting timeframe for adverse events meeting any serious criteria is described in section 7.2.3.1. The investigator will make every attempt to follow all subjects with non-serious adverse events for outcome.

7.3.1 Definition of an Overdose for This Protocol and Reporting of Overdose to the Sponsor-Investigator and to Merck

For purposes of this trial, an overdose of:

- pembrolizumab will be defined as any dose of 1,000 mg or greater (≥ 5 times the indicated dose).
- any standard treatment is any dose $>/= 20\%$ over the prescribed dose.

No specific information is available on the treatment of overdose of pembrolizumab. In the event of overdose, the subject should be observed closely for signs of toxicity. Appropriate supportive treatment should be provided if clinically indicated.

Overdoses of chemotherapy agents (oxaliplatin, capecitabine, epirubicin), will be managed in accordance with the respective product label.

If an adverse event(s) is associated with (“results from”) the overdose of a Merck product, the adverse event(s) is reported as a serious adverse event, even if no other seriousness criteria are met.

If a dose of Merck’s product meeting the protocol definition of overdose is taken without any associated clinical symptoms or abnormal laboratory results, the overdose is reported as a non-serious Event of Clinical Interest (ECI), using the terminology “accidental or intentional overdose without adverse effect.”

All reports of overdose with and without an adverse event must be reported within 24 hours to the Sponsor-Investigator and within 2 working days hours to Merck Global Safety. (Attn: Worldwide Product Safety; [contact])

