7.3.3 Immediate Reporting of Adverse Events to the Sponsor and to Merck

7.3.3.1 Serious Adverse Events

A serious adverse event is any adverse event occurring at any dose or during any use of Merck's product that:

- Results in death;
- Is life threatening;
- Results in persistent or significant disability/incapacity;
- Results in or prolongs an existing inpatient hospitalization;
- Is a congenital anomaly/birth defect;
- Is an other important medical event

• **Note:** In addition to the above criteria, adverse events meeting either of the below criteria, although not serious per ICH definition, are reportable to the Merck in the same timeframe as SAEs to meet certain local requirements. Therefore, these events are considered serious by Merck for collection purposes.

- Is a new cancer (that is not a condition of the study);
- Is associated with an overdose.

Refer to Table 8 for additional details regarding each of the above criteria.

For the time period beginning when the consent form is signed until treatment allocation, any serious adverse event, or follow up to a serious adverse event, including death due to any cause other than progression of the cancer under study that occurs to any subject must be reported within 24 hours to the Sponsor and within 2 working days to Merck Global Safety if it causes the subject to be excluded from the trial, or is the result of a protocol-specified intervention,

including but not limited to washout or discontinuation of usual therapy, diet, placebo treatment or a procedure.

For the time period beginning at treatment allocation/randomization through 90 days following cessation of treatment, or 30 days following cessation of treatment if the subject initiates new anticancer therapy, whichever is earlier, any serious adverse event, or follow up to a serious adverse event, including death due to any cause other than progression of the cancer under study whether or not related to the Merck product, must be reported within 24 hours to the Sponsor-Investigator and within 2 working days to Merck Global Safety.

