Additionally, any serious adverse event, considered by an investigator who is a qualified physician to be related to Merck product that is brought to the attention of the investigator at any time following consent through the end of the specified safety follow-up period specified in the paragraph above, or at any time outside of the time period specified in the previous paragraph also must be reported immediately to the Sponsor and to Merck Global Safety.

All subjects with serious adverse events must be followed up for outcome.

SAE reports and any other relevant safety information are to be forwarded to the Merck Global Safety [contact]

A copy of all 15 Day Reports and Annual Progress Reports is submitted as required by FDA, European Union (EU), Pharmaceutical and Medical Devices agency (PMDA) or other local regulators. Investigators will cross reference this submission according to local regulations to the Merck Investigational Compound Number (IND, CSA, etc.) at the time of submission. Additionally investigators will submit a copy of these reports to Merck & Co., Inc. (Attn: Worldwide Product Safety; [contact]) at the time of submission to FDA.

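### The SAE window in Section 7.2.5.3.1 conflicts with Sections 1.0, 2.1 and 7.3.3.1 when new therapy starts before day 90, and no adverse-event review is scheduled between the 30-day visit and day 90

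*Combined protocol and SAP*

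**What the plan says.** **SAE window.** Section 7.3.3.1 requires SAE reporting "through 90 days following cessation of treatment, or 30 days following cessation of treatment if the subject initiates new anticancer therapy, whichever is earlier". Section 1.0 gives the same rule for SAEs, and Section 2.1 gives it for SAEs and ECIs together. The visit section, 7.2.5.3.1, is worded differently: "SAEs that occur within 90 days of the end of treatment or before initiation of a new anti-cancer treatment should also be followed and recorded". It has no 30-day limit, and nothing says which of its two conditions prevails. Section 5.8 has a parenthesis with no new-therapy condition: "serious adverse events will be collected for 90 days after the end of treatment as described in Section 7.2.3.1". Section 7.3 sends the reader to the same number for the SAE timeframe, but 7.2.3.1 is now the laboratory section; SAE reporting is in 7.3.3.1.

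**ECI window.** Sections 2.1 and 7.3.3.2 agree with each other and with 7.3.3.1. Sections 5.8 and 7.2.5.3.1 do not mention ECIs.

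**Other adverse events.** Section 7.3 sets a shorter limit: "through 30 days following cessation of treatment, all adverse events must be reported by the investigator".

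**Follow-up of known events.** Section 7.2.5.3.1 follows events above Grade 1 until they settle to Grade 0-1 or new therapy begins. Section 7.3.3.1 says: "All subjects with serious adverse events must be followed up for outcome".

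**Scheduled contacts.** In Table 6 the last column with adverse-event review, blood count and chemistry is the 30-day safety visit (±7 days). After that, Section 7.2.5.3.2 says subjects "should be contacted by telephone every 12 weeks to assess for survival status". Table 6 adds only post-study anticancer therapy status to those calls.

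**Expected timing.** On events associated with pembrolizumab, Section 5.2.1.2.1 says: "These adverse events may occur shortly after the first dose or several months after the last dose of treatment".

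**The concern.** Two separate things looked wrong.

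First, a site that works from the visit section and one that works from the reporting section could close the SAE window on different days for the same subject. Section 8.2.3 does not settle the matter, because it plans counts, percentages and exact intervals without stating the period over which events count.

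Second, the protocol sets a 90-day collection period but schedules active ascertainment only up to about day 30. One ECI in Section 7.3.3.2 is a combination of transaminase, bilirubin and alkaline phosphatase values. It can be found only if blood is drawn, and no draw is scheduled after the 30-day visit. Since the protocol itself expects immune-related events months after the last dose, days 31 to 90 are a period in which events are anticipated but nobody is scheduled to ask about them.

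What is at stake is the completeness and comparability of the SAE and ECI rates, which Section 8.2.2 makes part of the safety assessment. The primary pCR analysis is not affected.

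**Working it through.** The plan gives no figure to reproduce here. The check compares the wording and then works out the day on which each rule closes.

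**1. Closing day of the SAE window.** Let *d* be the day after end of treatment on which new anticancer therapy starts. The values of *d* are assumptions, because the documents give no distribution for it.

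- Sections 1.0, 2.1 and 7.3.3.1: 90 if no new therapy starts; 30 if it does.
- Section 7.2.5.3.1, read as the earlier of its two conditions: min(90, *d*).
- Section 7.2.5.3.1, read as either condition being enough: 90 for any *d* below 90.

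| Assumed *d* | 7.3.3.1 | 7.2.5.3.1, earlier of | 7.2.5.3.1, either |
|---|---|---|---|
| none | 90 | 90 | 90 |
| 10 | 30 | 10 | 90 |
| 20 | 30 | 20 | 90 |
| 45 | 30 | 45 | 90 |
| 60 | 30 | 60 | 90 |
| 80 | 30 | 80 | 90 |

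The sections agree when no new therapy starts. Below day 90, the earlier-of reading matches 7.3.3.1 only at *d* = 30, and the either-condition reading never does. Depending on *d* and on the reading, 7.2.5.3.1 can be shorter or longer than 7.3.3.1.

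**2. Days without a scheduled review when no new therapy starts.** 90 − 30 = 60 days, and 60/90 = 67% of the window. With the ±7-day allowance on the safety visit, the gap runs from 90 − 37 = 53 to 90 − 23 = 67 days.

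**3. Where the first survival call falls.** The start point for the 12-week interval is not stated. Counted from the last dose, the call falls on day 12 × 7 = 84. Counted from the 30-day visit, it falls on day 30 + 84 = 114, after the window has closed. In neither case does Table 6 attach an adverse-event review to it.

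**4. What is captured without a prompt.** Section 7.3.3.1 has a provision with no time limit: an SAE that a physician investigator judges related, and that comes to that investigator's attention, must be reported even outside the window. This leaves two groups with no prompt on days 31-90: SAEs judged unrelated, which are reportable in the window but which nobody is scheduled to ask about, and the liver-test ECI.

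**5. Weight of one event.** If all 38 planned subjects are treated (an assumption), one event found or missed moves a rate by 1/38 = 2.6 percentage points. The exact 95% interval is 0.1-13.8% for 1/38 and 0.6-17.7% for 2/38. This shows the sensitivity of the rates. It does not estimate how many events would be missed.

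**The case against.** The strongest reply is that the defect is small and partly covered already. Several parts of that reply stand.

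- **A third rule in Section 5.8.** A reader might infer an unconditional 90-day rule. The parenthesis defers to another section, and its number follows a pattern: Section 7.3 uses the same outdated number, and 7.3.3.2 and 7.3.3.3 also point one level too low (7.2.1 and 7.2.3 for what are now 7.3.1 and 7.3.3). It is best read as shorthand for 7.3.3.1 with a stale reference. The clear conflict is between 7.2.5.3.1 and 7.3.3.1.
- **Conflicting ECI windows.** A reader might extend the conflict to ECIs. The documents do not support that, since Sections 2.1 and 7.3.3.2 agree. The exact interval in 8.2.3 is for events of clinical interest, so the wording conflict does not reach it; the lack of prompts does.
- **Late events lost.** This is too strong for related SAEs, which stay reportable at any time once known. Subjects who stop for reasons other than progression also have disease-status follow-up (Sections 2.1 and 5.8). Neither is a scheduled question about new adverse events, so the narrower point, passive ascertainment, remains.
- **Many subjects affected.** The 35% early-recurrence figure in Section 4.2.1 counts from surgery. It says nothing about new therapy within 90 days of the last dose.
- **The follow-up rules.** The rule for events above Grade 1 is general and the SAE rule is specific, so they can be read together. A clarifying sentence is enough.
- **The 30-day cut itself.** A reader might want 90 days for everyone. The cut is stated consistently in Sections 1.0, 2.1, 7.3.3.1 and 7.3.3.2. Replacing it is a trade-off, and keeping it is not an error.

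**Conclusion.** The point holds in two parts. (a) The SAE window in Section 7.2.5.3.1 cannot be reconciled as written with Sections 1.0, 2.1 and 7.3.3.1 for subjects who start new anticancer therapy before day 90. For an assumed start on day 60, the windows are 30 days against 60 or 90. (b) SAE and ECI collection extends to day 90 when no new therapy starts, but about 60 of those days (53-67 with the visit allowance) have no scheduled adverse-event review or laboratory test.

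SAE and ECI rates may therefore be under-ascertained. How far, and whether sites would in fact differ, cannot be estimated from the documents: they give neither the number of subjects who start new therapy before day 90 nor the rate of events on days 31-90. The start days used above are illustrations. The change is worth making because it costs little; it does not call the design into question.

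**What to change.** 1. Reconcile Sections 5.8 and 7.2.5.3.1 with 1.0, 2.1 and 7.3.3.1 so that one SAE window is stated throughout, and correct the references to 7.2.3.1 in Sections 5.8 and 7.3.
2. State in 7.2.5.3.1 that stopping follow-up of events above Grade 1 at new therapy does not override the follow-up of SAEs for outcome in 7.3.3.1.
3. Record the start date of new anticancer therapy, and flag any event after it in the tables.
4. Define the start point of the 12-week calls, time the first at about the end of the 90-day window, and give it a scripted SAE/ECI question. Mark the adverse-event review row in that column of Table 6.
5. State the counting window for SAEs and ECIs in Section 8.2.3.

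The cost is a text amendment, plus one added question and fixed timing for a call already planned. Some events reported on that call may be confounded by new therapy, which the flag in item 3 makes visible.
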